10.10.3. Reporting of Non-Serious Adverse Event

All Non-Serious Adverse Events will be documented on the Adverse Event Page(s) of the CRF and reported properly to the local regulatory authority.

10.12. Sponsor Reporting Requirements to Regulatory Authorities

During the course of the study, the Sponsor will report All Adverse Events to the Local Health Authorities, in accordance with the Local Timeframes for Reporting.

10.13. Breaking Randomization Code

Not Applicable.

Study Protocol: EVA_CLEAR_11022017 Version Number: Final V2.0/19-Jun-2017

11. Ethical and Regulatory Standards

11.1. Ethical principles

This study will be conducted in accordance with the 18th World Medical Assembly (Helsinki, 1964) and all subsequent amendments and ICH guidelines for Good Clinical Practice (ICH-E6). Study team will ensure all necessary regulatory submissions (e.g.: IRB/IEC) are performed in accordance with local regulations including local data protection regulations.

11.2. Laws and Regulations

This Clinical Trial will be conducted in compliance with all applicable international laws and regulations, and national laws and regulations of Egypt in which the Clinical Trial is performed, as well as any applicable guidelines.

11.3. Data Informed Consent

The Investigator (according to applicable regulatory requirements), or a person designated by the Investigator, and under the Investigator's responsibility, should fully inform the patient of all pertinent aspects of the Clinical Trial including the written information giving approval/favorable opinion by the Ethics Committee (IRB/IEC). All participants should be informed to the fullest extent possible about the study, in language and terms they are able to understand.

Prior to a patient's participation in the Clinical Trial, the written Informed Consent Form must be signed, name filled in and personally dated by the patient or by the patient's legally acceptable representative and by the person who conducted the informed consent discussion. A copy of the signed and dated written Informed Consent Form will be provided to the patient.

The Informed Consent Form used by the Investigator for obtaining the patient's informed consent must be reviewed and approved by the Sponsor prior to submission to the appropriate Ethics Committee (IRB/IEC) for approval/favorable opinion.

11.4. Institutional Review Board/Independent Ethics Committee (IRB/IEC)

The Investigator or the Sponsor must submit this Clinical Trial Protocol to the appropriate Ethics Committee (IRB/IEC).Written dated approval/favorable opinion signed by the Chairman with Ethics Committee (IRB/IEC) composition must be obtained.

Investigational Product will not be released at the study site and the Clinical Trial will not start until a copy of this written and dated approval/favorable opinion has been received by the Sponsor.

During the Clinical Trial, any amendment or modification to the Clinical Trial Protocol should be submitted to the Ethics Committee (IRB/IEC). It should also be informed of any event likely to affect the safety of patients or the continued conduct of the Clinical Trial, in particular any change in safety.

If requested, a summary of the Clinical Trial's outcome at the end of the Clinical Trial is sent to the Ethics Committee (IRB/IEC).

11.5. Discontinuation / Withdrawal of participants from study

Each participant has the right to withdraw from the study at any time. In addition, the investigator may discontinue a participant from the study at any time if the investigator considers it necessary for any reason including:

- 1. Ineligibility (either arising during the study or retrospective having been overlooked at screening)
- 2. Significant protocol deviation
- 3. Significant non-compliance with treatment regimen or study requirements
- 4. Disease progression which requires discontinuation of the study medication or results in inability to continue to comply with study procedures.
- 5. Consent withdrawn.
- 6. Lost to follow up

The reason for withdrawal will be recorded in the CRF.

If the participant is withdrawn due to an adverse event, the investigator will arrange for follow-up visits or telephone calls until the adverse event has resolved or stabilized. Patients who withdraw from the study will not be replaced.

12. Quality Control and Quality Assurance

- 12.1. Quality Control
 - 12.1.1. In Process Quality Control of Biometrics

As per DataClin CRO SOPs, quality control by an independent qualified reviewer is performed on all biometrics related documents developed internally. This includes study protocol, case report form, informed consent form and study plans. In addition to these documents, database QC is performed automatically (programmed edit checks) and manually (manual review of line listings) to ensure that data is complete and consistent.

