8.3. Analysis Population

The obtained clinical data will be analyzed on an intention-to-treat basis. Primary analysis will be done by intention-to-treat including all eligible enrolled patients with at least one treatment dose and post first assessment score (CDAI and HAQ) attending any post treatment visit and efficacy variables will be analyzed using the last-observation-carried-forward convention (LOCF).

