9.2. Mode of Administration

Arthfree (Leflunomide 20mg)

Study Protocol: EVA_CLEAR_11022017

Dose: 1 tablet once daily, should be swallowed whole with sufficient amounts of liquids. The extent of Leflunomide absorption is not affected if taken with meals. Doses higher than 20 mg/day are not recommended. Improvement in the rheumatoid condition usually starts after 4 to 6 weeks and may further improve up to 4 to 6 months.

Loading dose: a tablet of Leflunomide 100 mg for three days. should be swallowed whole with sufficient amounts of liquids. The extent of Leflunomide absorption is not affected if taken with meals.

Due to the long half-life in patients with rheumatoid arthritis and recommended dosing interval (24 hours), a loading dose is needed to provide steady-state concentrations more rapidly.

10. Pharmacovigilance

For Safety Reference; this study will be conducted consistent with The International Conference on Harmonization Guideline E2A and 21 CFR Part 312 and WHO Guidelines.

Safety assessments will consist of monitoring and recording adverse events; including serious and non-serious adverse events, measurement of protocol-specified safety laboratory assessments, measurement of Protocol-Specified Vital Signs and other Protocol-Specified Measures that are deemed critical to the safety evaluation of the study.

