10.2. Adverse Events Monitoring

All AEs regardless of seriousness or relationship to Medicinal Product (MP), spanning from the signature of the informed consent form, until the end of the study as defined by the protocol for that patient, are to be recorded on the corresponding page(s) included in the CRF and reported as described in the following sections.

For all adverse events, the investigator must pursue and obtain information adequate to determine the outcome of the adverse event and to assess whether it meets the criteria for classification as a serious adverse event requiring immediate notification to Sponsor or its designated representative.

For all adverse events, sufficient information should be obtained by the investigator to determine the causality of the adverse event. The investigator is required to assess causality. For adverse events with a causal relationship to the MP, Follow-Up by the investigator is required until the event or its sequelae resolve or stabilize at a level acceptable to the investigator, and Sponsor concurs with that assessment. This may imply that observations will continue beyond the last planned visit per protocol, and that additional investigations may be requested by the Monitoring Team up to as noticed by the sponsor

Whenever possible, diagnosis or single syndrome should be reported instead of symptoms. The Investigator should specify the date of onset, intensity, action taken with respect to MP, corrective treatment/therapy given, additional investigations performed, outcome and his/her opinion as to whether there is a reasonable possibility that the AE was caused by the MP.

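### Section 11.5 does not separate stopping leflunomide from leaving the study, and nothing provides for outcome, laboratory or routine new-AE collection to week 36 after a patient is removed

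*Combined protocol and SAP*

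**What the plan says.** Section 11.5 gives a broad, discretionary power: "the investigator may discontinue a participant from the study at any time if the investigator considers it necessary for any reason including" six listed grounds. Three of them matter here:

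- item 2: "Significant protocol deviation";
- item 3: "Significant non-compliance with treatment regimen or study requirements";
- item 4: "Disease progression which requires discontinuation of the study medication or results in inability to continue to comply with study procedures".

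The reason for withdrawal goes into the CRF, and withdrawn patients are not replaced. The only follow-up that section 11.5 itself describes is for one group, and it lasts only until the event in question settles: "If the participant is withdrawn due to an adverse event, the investigator will arrange for follow-up visits or telephone calls until the adverse event has" (the sentence closes by naming resolution or stabilisation).

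Section 10.2 records AEs from consent "until the end of the study as defined by the protocol for that patient". Section 8.3 states: "The obtained clinical data will be analyzed on an intention-to-treat basis". It defines that set as eligible patients with at least one dose and a post-treatment CDAI and HAQ assessment, with LOCF for efficacy variables. Sections 8.4.1 and 8.5.1 place the primary outcomes, CDAI and HAQ, at baseline and week 36. The schedule in section 7.2 has six visits, no early-termination visit, and a completion form at Visit 6 only.

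**The concern.** The study is observational, and it names treatment duration and the reasons for adjusting treatment among its secondary endpoints (section 8.4.2). Patients who stop leflunomide are part of what it sets out to describe. A rule that lets sites end participation because the regimen was not followed, or because the disease progressed and the drug was stopped, belongs to a per-protocol way of working. It sits badly with a declared intention-to-treat analysis.

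What is at stake is the primary endpoint. A patient removed under item 4 has, by definition, progressing disease. If the week-36 CDAI and HAQ are then not measured, missingness depends on outcome and the analysis substitutes an earlier score. Section 8.8 leaves the handling of missing values to the SAP, but no analysis can recover a value that could have been collected and was not. There is also a safety side: AE frequency is an endpoint (section 8.4.3), and new non-serious events and scheduled AST and ALT after removal have no clear provision. With 24 sites and a discretionary rule, practice may also differ between sites.

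**Working it through.** **1. What continues after removal.** Setting the sections side by side:

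| Data | Provision after removal from the study |
|---|---|
| CDAI, HAQ | None found |
| Scheduled laboratory tests | None found |
| AE that caused withdrawal | Followed until resolved or stable (11.5) |
| AE causally related to the drug | Followed until resolved or stable, if need be past the last planned visit (10.2) |
| SAE suspected to be related | Reported at any time after the reporting period (10.3) |
| New AE, any relationship | Unclear |

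The last row is unclear for three reasons. Section 10.2 ties the window to the patient's own end of study without saying whether that means removal or week 36. The synopsis visit table labels week 36 as EOS, which favours the later date. Section 10.10.1 requires all AEs after prescription to be reported, with no on-study condition. Section 10.3 refers to a follow-up period specified in the protocol, but none is specified.

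Item 4 has an ambiguity of its own. Section 10.1.1 lists worsening of the underlying disease as an example of an AE, which would bring item 4 under the follow-up clause of 11.5. Section 10.7 separates withdrawal for an AE from withdrawal for insufficient response, which points the other way.

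**2. The plan's own figures.** Inputs from section 8.1: two-sided 5%, power 80%, Wilcoxon signed-rank test, effect size 0.158, drop-out 20%.

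- Paired t-test power by the noncentral t, with the Wilcoxon efficiency for normal data, 3/π = 0.955: N = 332. This matches the plan.
- Inflation as the plan does it: 332 × 1.2 = 398.4, stated as 398 and rounded to 400. (332/0.8 would be 415; that is a separate matter and does not bear on this point.)

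**3. Upper bound on the number affected.** Planned drop-out: 0.20 × 400 = 80, leaving 400 − 80 = 320 with an observed week-36 value. The 80 covers every cause, including consent withdrawal and loss to follow-up. The share due to items 2 to 4 is not given, so under the planned drop-out it lies anywhere from 0 to 80.

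**4. Power or bias?** At effect size 0.158, power is 80.1% with 332 and 78.6% with 320 observed. Precision barely changes, so the issue is bias. If a fraction p of the analysis set carries an LOCF value that differs on average by D from the value that would have been measured, the mean shifts by p × D. With p at most 80/400 = 0.20, the shift is at most one fifth of D. The documents give no D. Its sign is also open, since a patient may worsen further or improve on another treatment.

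**5. What one removal costs.** From the schedule (weeks 6, 12, 20, 28, 36):

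| Last visit attended | Weeks unobserved | Visits lost |
|---|---|---|
| Visit 2 | 36 − 6 = 30 | 4 |
| Visit 3 | 36 − 12 = 24 | 3 |
| Visit 4 | 36 − 20 = 16 | 2 |
| Visit 5 | 36 − 28 = 8 | 1 |

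In each row the week-36 value is among those lost.

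**The case against.** The strongest reply is that section 11.5 only permits removal. Nothing obliges a site to remove a patient who stops leflunomide, and nothing says that collection then ceases. A patient who stops and still attends every visit breaches no rule. Other sections treat the drug apart from study exit: section 10.2 asks for the action taken with the product, and section 8.4.2 describes treatment duration. Removed patients with a dose and a post-treatment assessment stay in the section 8.3 set. All of this stands, and it limits the point to a permission plus an absent provision.

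Four stronger readings are tempting, and the documents do not support them:

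- *AE collection ends at removal.* Sections 10.2, 10.3, 10.10.1 and 11.5 all keep some collection alive, and the window may run to week 36.
- *The rule removes the patients doing worst.* That fits item 4. Deviation and non-compliance need not follow outcome, and patients withdrawn for an AE do get follow-up.
- *The protocol's own half-life statement shows that late events will be missed.* The phrase "Due to the long half-life in patients with rheumatoid arthritis" appears in section 9.2 only to justify a loading dose. Nothing there concerns events after stopping.
- *Removal contradicts the physician's sole decision on treatment.* Those statements concern prescribing, not study exit.

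A further objection also stands. The endpoints concern patients treated with leflunomide, and there is no comparator. A week-36 score obtained on a replacement drug could be credited to leflunomide, so collecting such values without saying how they will be shown would exchange one problem for another.

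**Conclusion.** The point holds as a gap. Section 11.5 merges stopping the drug with leaving the study, permits removal on grounds that an observational, intention-to-treat study does not need, and is matched by no provision for CDAI, HAQ, scheduled laboratory or routine new-AE data to week 36. Where a site uses the permission, obtainable week-36 values become LOCF values, and under item 4 that loss depends on outcome. Whether the AE window closes at removal or at week 36 is unresolved.

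The size cannot be fixed from the documents. The ceiling under the planned drop-out is 80 of 400 patients (20%), of whom an unknown part would leave under items 2 to 4. The effect on power is small (78.6% against 80.1%); the effect on bias is at most one fifth of an unknown average LOCF error. This rests on two assumptions: that sites use the permission, and that they collect nothing further once a patient is removed. The second is inferred from the lack of any later schedule; the text does not state it. Section 10.11 was not in the text available to me; by its title it deals with SAE reporting only.

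**What to change.** In section 11.5, separate stopping leflunomide from leaving the study:

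- State that protocol deviation, non-compliance with the regimen, and stopping leflunomide for any reason do not by themselves end data collection.
- Ask these patients to continue the scheduled visits to week 36, as far as they are able and willing, with AE, laboratory, CDAI and HAQ data collected and the date and reason of the stop recorded.
- Keep consent withdrawal, loss to follow-up and inability to comply with study procedures as exits.
- Flag values obtained after stopping or switching, and show results with and without them.
- Reconcile 11.5 with 8.3, 10.2, 10.3 and 10.7, and say in 10.2 whether a patient's AE window ends at removal or at week 36.

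The decision to stop treatment remains with the physician and is not changed.

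The cost is a wording change and an instruction to sites. The visits are already in the schedule, though the documents say nothing about budget. The downside is some site effort and incomplete attendance after stopping, so part of the loss will remain.

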MEDICINAL PRODUCT	Arthfree (Leflunomide 20mg) Dose: 1 tablet once daily, should be swallowed whole with sufficient amounts of liquids. The extent of Leflunomide absorption is not affected if taken with meals. Doses higher than 20 mg/day are not recommended. Improvement in the rheumatoid condition usually starts after 4 to 6 weeks and may further improve up to 4 to 6 months. Loading dose: a tablet of Leflunomide 100 mg for three days. should be swallowed whole with sufficient amounts of liquids. The extent of Leflunomide absorption is not affected if taken with meals. Due to the long half-life in patients with rheumatoid arthritis and recommended dosing interval (24 hours), a loading dose is needed to provide steady-state concentrations more rapidly. Patients will be prescribed Arthfree (Leflunomide) at the sole decision of the treating physician.					
	This phase IV study will last for 9 months in addition to recruitment period of 3 months. A total of 6 visits will be performed as shown in the table below;					
	Visit 1	Visit 2	Visit 3	Visit 4	Visit 5	Visit 6
DATA COLLECTION SCHEDULE	Baseline & ICF signing	Week 6 (± 2 weeks)	Week 12 (± 2 weeks)	Week 20 (± 2 weeks)	Week 28 (± 2 weeks)	Week 36 (± 2 weeks) EOS
	Clinical Assessment	Clinical Assessment	Clinical Assessment if applicable Clinica Assessm		Clinical Assessment	
	Lab Data	Lab Data Lab Data if applicable Lab		Lab Data		
	Safety Data					
DATA TO BE COLLECTED (FOR PRIMARY AND SECONDARY OBJECTIVES)**	 At Baseline Visit: Data on Informed consent, Inclusion and exclusion criteria, Demographics, Smoking status, Alcohol consumption, Medical history, Gynecological History for female patients only, Concomitant medications, Laboratory tests and Poor prognostic factors will be 					

	collected along with RA history.				
	Disease assessment (CDAI) and Physical examination will be done and also Vital signs will be recorded.				
	Patients will fill Health Assessment Questionnaire (HAQ Disability				
	Index) and related data will be recorded.				
	At Visit 2 (Week 6 ± 2 weeks) & Visit 3 (Week 12 ± 2 weeks) & Visit				
	4 (Week 20 ± 2 weeks) & Visit 5 (Week 28 ± 2 weeks):				
	Data on Concomitant medications and Laboratory tests will be collected.				
	Disease assessment (CDAI) and Physical examination will be done and also Vital signs will be recorded.				
	Patients will fill Health Assessment Questionnaire (HAQ Disability Index) and related data will be recorded.				

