7.2.2. Data Collection Process

Data will be collected using NCR CRF according to the below manner;

At Baseline Visit:

Data on Informed consent, Inclusion and exclusion criteria, Demographics, Smoking status, Alcohol consumption, Medical history, Gynecological History for female patients only, Concomitant medications, Laboratory tests and Poor prognostic factors will be collected along with RA history.

Disease assessment (CDAI) and Physical examination will be done and also Vital signs will be recorded.

Patients will fill Health Assessment Questionnaire (HAQ Disability Index) and related data will be recorded.

At Visit 2 (Week 6 ± 2 weeks) & Visit 3 (Week 12 ± 2 weeks) & Visit 4 (Week 20 ± 2 weeks) & Visit 5 (Week 28 ± 2 weeks):

Data on Concomitant medications and Laboratory tests will be collected.

Disease assessment (CDAI) and Physical examination will be done and also Vital signs will be recorded.

Patients will fill Health Assessment Questionnaire (HAQ Disability Index) and related data will be recorded.

Data on Adverse events/Serious adverse events experienced by patient since the previous visit will be documented.

At Visit 6 (Week 36 ± 2 weeks):

Data on Concomitant medications and Laboratory tests will be collected.

Disease assessment (CDAI) and Physical examination will be done and also Vital signs will be recorded.

Patients will fill Health Assessment Questionnaire (HAQ Disability Index) and related data will be recorded.

Data on Adverse events/Serious adverse events experienced by patient since the previous visit will be documented.

Study Completion Form will be also filled.

Data on Adverse events/Serious adverse events experienced by patient since the previous visit will be documented.

Study Completion Form will be also filled.

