10.7. Withdrawal Due to Adverse Events

Withdrawal due to adverse event should be distinguished from withdrawal due to Insufficient Response, according to the definition of adverse event noted earlier, and recorded on the appropriate Adverse Event CRF Page.

When a subject withdraws due to a serious adverse event, the serious adverse event must be reported in accordance with the reporting requirements defined below.

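### No CDAI, HAQ or Study Completion Form is scheduled at early withdrawal, so for patients who worsen and leave between visits LOCF can carry an earlier, better score

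*Combined protocol and SAP*

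**What the plan says.** **At withdrawal.** Section 11.5 lists disease progression among the reasons for discontinuing a participant. The data it asks for are limited: "The reason for withdrawal will be recorded in the CRF". Visits or calls after withdrawal are arranged only for adverse-event withdrawals, and neither CDAI nor HAQ is named. Withdrawn patients are not replaced. Section 10.7 also expects some patients to leave for lack of effect: "Withdrawal due to adverse event should be distinguished from withdrawal due to Insufficient Response".

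**Schedule.** CDAI and HAQ are due at baseline and at Visits 2 to 6 (weeks 6, 12, 20, 28 and 36). Section 7.2.2 repeats for each visit "Disease assessment (CDAI) and Physical examination will be done and also Vital signs will be recorded" and "Patients will fill Health Assessment Questionnaire (HAQ Disability Index) and related data will be recorded". The instruction "Study Completion Form will be also filled" appears only under Visit 6, and both schedule tables (Synopsis and 7.2.1) mark that form only in the Visit 6 column. The Synopsis labels that visit "Week 36 (± 2 weeks) EOS". No table has an early-withdrawal column.

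**Analysis.** Under section 8.3, "efficacy variables will be analyzed using the last-observation-carried-forward convention (LOCF". The primary set requires at least one dose and a CDAI and HAQ score after treatment. Section 8.4.1 makes the primary endpoints the change in CDAI and HAQ from baseline to week 36, together with the CDAI severity categories. Section 8.2 states that randomization does not apply. Section 8.8 leaves further missing-data rules to a SAP.

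**The concern.** A patient who is doing badly may not wait for the next visit. If that patient stops between visits, the plan asks for a reason but no score. The most recent CDAI and HAQ then stand for week 36, although they may have been taken before the deterioration that led the patient to leave.

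The primary result is a change from baseline with no randomised comparator, so there is no control group in which such an error could cancel. It would enter the mean change in CDAI and HAQ directly and could place a patient in a lower CDAI activity category than the one held at exit.

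A SAP written later can choose a different missing-data method, but it cannot recover a score that was never taken. The gap therefore has to be closed in the schedule.

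**Working it through.** **1. Age of the carried score.** Nominal visit weeks are 0, 6, 12, 20, 28 and 36, so the gaps are 6, 6, 8, 8 and 8 weeks. With ±2-week windows the longest gap is (later visit + 2) − (earlier visit − 2), with baseline fixed at 0. That gives 8, 10, 12, 12 and 12 weeks. Nothing is carried across the first gap, because there is no post-treatment score yet. After Visit 2 the score can be up to 8 weeks old at nominal times and up to 12 with windows. The Synopsis also has an entry "Clinical Assessment if applicable" for some mid-study visits. The table is broken in the supplied text, so the visits it covers cannot be read with certainty; if an assessment were skipped, the carried score would be older.

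**2. The plan's own figures (8.1).** Paired noncentral-t power with n multiplied by the Wilcoxon efficiency 3/π, effect size 0.158 and two-sided 5% gives n = 332 (power 0.801). The stated 398 is 332 × 1.2 = 398.4. Neither figure depends on an exit visit. Expected drop-outs are 0.20 × 400 = 80.

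**3. Who is affected.**

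| When and why the patient leaves | Effect under 8.3 |
|---|---|
| At a scheduled visit | Current score exists and is carried; not affected |
| Between visits, for progression or insufficient response | Earlier, possibly better score is carried |
| Between visits, for another reason | Score may be old, but the patient need not be worse |
| Before Visit 2 | No post-treatment score; outside the primary set |

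**4. Size for the second row.** The documents give only the 20% drop-out and the 0.158. The share leaving for failure (25–75%), the worsening since the last score (5–10 CDAI points) and the SD of change (12) are assumptions.

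Overstatement in points = 0.20 × share × worsening. Divide by 12 for SD units.

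| Case | Points | SD units | Relative to 0.158 |
|---|---|---|---|
| Low | 0.20 × 0.25 × 5 = 0.25 | 0.021 | 13% |
| Midpoint | 0.20 × 0.50 × 7.5 = 0.75 | 0.0625 | 40% |
| High | 0.20 × 0.75 × 10 = 1.5 | 0.125 | 79% |

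At the midpoint, an SD of 10 gives 0.075 (47%) and an SD of 15 gives 0.05 (32%).

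These are upper values, because they treat every failure leaver as leaving between visits with a score to carry. If half leave at a visit, they halve to 0.010, 0.031 and 0.0625 SD (7%, 20% and 40% of 0.158).

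**5. A second set of assumptions.** If 10–50% of the 80 (8 to 40 patients) leave between visits because of worsening, and LOCF misses 0.25–1.0 SD in each, the overstatement runs from 0.20 × 0.10 × 0.25 = 0.005 SD (3% of 0.158) to 0.20 × 0.50 × 1.0 = 0.10 SD (63%).

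**The case against.** The strongest reply is that CDAI and HAQ are due at every visit. A patient whose progression is found at a visit, and who is withdrawn there, has a same-day score, and LOCF carries it. That stands. A reader might infer that every early leaver is scored before the worsening; the schedule does not support this.

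Nor is the error one-way across all leavers. Section 11.5 lists several reasons unrelated to worsening, such as ineligibility and protocol deviation. Section 9.2 says improvement may continue for 4 to 6 months, so an old score can understate benefit in a patient who leaves for such a reason. Those who leave before Visit 2 are excluded, which is selection and not LOCF.

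A reader might also infer that the reason for leaving is not captured before week 36. The documents do not show this: section 11.5 has it recorded in the CRF whenever withdrawal occurs, and the CRF itself is not supplied.

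It can further be said that the harm runs through LOCF, and that an exit score at week 16, say, still stands in for week 36. Both are true. But the missing score would be missing under any method, and the status at exit is a better last observation than one taken before the deterioration. Finally, some patients who refuse or are lost to follow-up will never supply a score. That limits the gain but does not remove it.

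**Conclusion.** The point holds for a defined group: patients who leave between scheduled visits because of progression or insufficient response. For them the plan can carry an earlier, better CDAI and HAQ to week 36, which biases the mean change and the CDAI categories towards benefit. A related loss is that patients who leave before Visit 2 drop out of the primary set.

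The size is not known from the documents. Under the first set of assumptions the overstatement is at most 0.02–0.125 SD, midpoint 0.0625, and about half that if half of these patients leave at a visit. The second set reaches down to 0.005 SD, which is negligible. Both calculations use absolute change, whereas the endpoint is relative change, and no figure is offered for HAQ.

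The ratio to 0.158 only gives scale. That figure is the effect the study is sized to detect, not the improvement expected, so the percentages should not be read as the share of the reported result that is bias. Nothing here shows that a significance test would be reversed. This is a cheap improvement to the plan.

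**What to change.** - **Synopsis table, 7.2.1 and 7.2.2:** relabel the last column and visit as Visit 6 (week 36) or early withdrawal, whichever comes first.
- **11.5:** ask that CDAI, HAQ, adverse events, concomitant medication and the Study Completion Form (date and reason) be recorded at withdrawal in patients willing to attend.
- **8.3:** state that this exit score counts as a post-treatment assessment and is the last observation for patients who leave early.

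The cost is a relabelled column, a sentence each in 11.5 and 8.3, and a small number of extra contacts: at most about 80 patients at the planned drop-out rate, using assessments already made at every visit. The sample size of 400 is unchanged. Patients who refuse or are lost to follow-up will still lack the score, and the exit score shows status at exit, not at week 36. The reported improvement may be slightly smaller.
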